## **2.5 Determination of Sample Size**

### **Part 1 (Pharmacokinetic Assessment)**

From Study LAM-IV-111, the mean±standard deviation  $AUC_{0-t}$  was  $3.099\pm 2.888$  ng.hr/mL and  $C_{max}$  was  $0.296\pm 0.177$  ng.hr/mL for a 1000mg single dose of lanthanum carbonate in subjects with renal failure who were receiving dialysis. Assuming the standard deviations from Study LAM-IV-111, a sample size of 8 subjects will have 80% assurance that the 2-sided 95% confidence interval for the  $AUC_{0-t}$  will be no wider than  $\pm 2.86$  ng.hr/mL and 80% assurance that 2-sided 95% confidence interval for  $C_{max}$  is no wider than  $\pm 0.18$  ng.hr/mL.

### **Parts 2 and 3 [Efficacy – Percentage of Subjects Achieving Kidney Disease Outcome Quality Initiative (KDOQI) Target for Serum Phosphorus]**

Originally, the sample size of at least 50 subjects for the PP set had been chosen based on practical considerations and on agreement with the Paediatric Committee of the European Medicines Agency. In order to obtain a PP Set of 50 subjects, a sample size of approximately 72 subjects were to be enrolled in Part 2. This assumed 70% of the subjects are eligible for the PP Set. This sample size has 81% power to show that the lower limit of the 95% confidence interval for the difference (LC – CC) in the percentage of subjects achieving serum phosphorus target is above the non-inferiority margin of -18%.

However, given the extreme difficulty in recruiting enough subjects to obtain at least 50 subjects for the PP set for the assessment of non-inferiority, serious consideration had to be given to adjust the sample size and focus of the study to safety, in order to complete it. The sample size has been adjusted to include at least 32 subjects, who complete 8 weeks of treatment with lanthanum carbonate and are assessable for the primary endpoint. This study is still useful in collecting information, where there is a void, regarding the use of lanthanum in the paediatric population.

For the investigation of safety profile in hyperphosphatemic children and adolescents with chronic kidney disease (CKD) on dialysis treated with lanthanum carbonate, a sample size of 32 subjects is necessary in order to observe at least one event with a true event rate of 5% at a probability of 80.6%.

## **2.6 Multiplicity Adjustments for Type I Error Control**

There is a single primary objective that specifies summarization of the percentage of subjects achieving age-specific KDOQI targets for serum phosphorus in hyperphosphatemic children and adolescents with CKD who are on dialysis, following 8 weeks of treatment with lanthanum carbonate. Consequently, no adjustment for multiplicity is required.

### **3. OBJECTIVES**

#### **3.1.1 Primary Objectives**

To summarize the percentage of subjects achieving age-specific Kidney Disease Outcomes Quality Initiative (KDOQI) targets for serum phosphorus in hyperphosphatemic children and adolescents with chronic kidney disease (CKD) who are on dialysis, following 8 weeks of treatment with lanthanum carbonate.

#### **3.1.2 Secondary Objectives**

1. To investigate the safety profile in hyperphosphatemic children and adolescents with CKD on dialysis treated with calcium carbonate and/or lanthanum carbonate.
2. To summarize the percentage of subjects achieving KDOQI targets for serum phosphorus in hyperphosphatemic children and adolescents with CKD who are on dialysis following treatment with calcium carbonate for 8 weeks and lanthanum carbonate for 8 weeks.
3. To assess mean changes from baseline in serum phosphorus, calcium and calcium-phosphorus product in hyperphosphatemic children and adolescents with CKD who are on dialysis, following treatment with lanthanum carbonate for 8 weeks.
4. To summarize mean changes from baseline in serum phosphorus, calcium and calcium-phosphorus product in hyperphosphatemic children and adolescents with CKD who are on dialysis, following treatment with calcium carbonate for 8 weeks and lanthanum carbonate for 8 weeks.
5. To describe the pharmacokinetics (maximum plasma concentration [Cmax] and area under the plasma concentration-time curve from time zero to the time of the last quantifiable concentration [AUC0-t; body weight-normalized) of lanthanum carbonate in hyperphosphatemic children and adolescents aged 10 years to <18 years with CKD who are on dialysis, after a single dose of lanthanum carbonate oral powder formulation is administered (Part 1 of the study).
6. To investigate the efficacy (serum phosphorus, calcium, and calcium phosphorus product) and safety of up to 8 months of treatment with lanthanum carbonate in children and adolescents aged 10 years to <18 years (Parts 2 and 3 of the study combined).
7. To investigate biochemical markers of bone metabolism including bone alkaline phosphatase (ALP), tartrate-resistant acid phosphatase (TRAP), osteocalcin, fibroblast growth factor 23 (FGF-23), parathyroid hormone (PTH), sclerostin and fetuin-A in children and adolescents aged 10 years to <18 years with CKD who are on dialysis.
8. To investigate growth in children and adolescents aged 10 years to <18 years with CKD who are on dialysis and weight.

## **4. SUBJECT POPULATION SETS**

### **4.1 Screened Set**

The Screened Set is defined as the set of subjects who have signed informed consent.

### **4.2 Enrolled Set**

The Enrolled Set is defined as subjects who have signed informed consent and have begun some study procedures (eg, dispensed investigational product, current drug has been withdrawn).

### **4.3 Safety Analysis Sets**

#### **4.3.1 Safety Analysis Set 1 (SAS1)**

Safety Analysis Set 1 is defined as enrolled subjects who have taken 1 dose of investigational product in Part 1 and who have completed at least 1 follow-up safety assessment.

#### **4.3.2 Safety Analysis Set 2 (SAS2)**

Safety Analysis Set 2 is defined as enrolled subjects who have taken 1 dose of investigational product in Part 2 or Part 3 and who have completed at least 1 follow-up safety assessment.

It is noted that safety assessments from the period when a subject is exposed to calcium carbonate will be summarized for calcium carbonate treatment and will include events occurring during calcium carbonate therapy prior to receiving lanthanum carbonate or going off study. Safety assessments from the period when a subject is exposed to lanthanum carbonate will be summarized for lanthanum carbonate treatment.

#### **4.3.3 Safety Completer Set (SCS)**

The Safety Completer Set is defined as subjects who receive at least 8 weeks of lanthanum carbonate treatment from either Part 2 or Part 3 of the study.

### **4.4 Full Analysis Set (FAS)**

The Full Analysis Set is defined as subjects who have taken at least 1 dose of investigational product and who have at least 1 phosphate assessment during Part 2 or Part 3.

#### **4.5 Per-protocol Set 1 (PP1)**

Per-protocol Set 1 is defined as subjects in the Full Analysis Set who complete 8 weeks of calcium carbonate treatment followed by 8 weeks of lanthanum carbonate treatment and who have serum phosphate assessment data available to allow summarizing the percentage of subjects achieving age-specific KDOQI target. Only subjects who have serum phosphate levels above the age-specific KDOQI targets at study entry and between the calcium carbonate treatment and lanthanum carbonate treatment at Visit 2.4 or the visits during washout will be included in this

set. Further details are described in the Evaluable Subjects Determination Plan which can be found in Section 21.

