#### **7.1.2.3 Part 2a: Visit 2.4 (Week 8; ±3 Days)**

- Vital signs, height, and weight will be measured.
- Blood samples will be taken for biochemistry, and biochemical bone markers.
- Investigational product will be collected and drug accountability performed.
- Any AEs that occurred since the last visit will be recorded.
- A review of any concomitant medication taken since the last visit will be performed and changes recorded.
- Confirmation of dialysis adequacy and dietary advice will be made.
- If phosphate levels remain >6.0mg/dL (1.94mmol/L) for subjects aged under 12 years or >5.5mg/dL (1.78mmol/L) for subjects aged 12 years and older, the subject may be dispensed lanthanum carbonate at a total daily dose of 1500mg to be taken with meals. If phosphate levels are below these levels the subject must enter a washout period of up to 3 weeks or until the targeted levels are reached, whichever is earliest. If a subject has started lanthanum carbonate based on local laboratory results, the subject will be allowed to continue the study even if central laboratory results do not agree.

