#### **7.1.2.4 Part 2a: Washout (W2)**

Subjects will be asked to stop taking calcium carbonate and will not be taking a phosphate binder, for up to 3 weeks or until phosphate levels, to be measured locally, of >6.0mg/dL (1.94mmol/L) for subjects aged under 12 years or >5.5mg/dL (1.78mmol/L) for subjects aged 12 years and older are reached, whichever is sooner. The phosphate level should be confirmed by taking a sample (between 0.1-0.7mL depending on each country's specific requirements) which will be analyzed by the central laboratory. If a subject has started lanthanum carbonate based on local laboratory results, the subject will be allowed to continue the study even if central laboratory results do not agree.

Any AEs or changes to concomitant medication will be recorded.

Subjects who complete the 3-week washout (W2) will be dispensed lanthanum carbonate at a starting daily dose of 1500mg to be taken with meals.

Subjects whose phosphate levels do not rise above 6.0mg/dL (1.94mmol/L) for subjects aged under 12 years or >5.5mg/dL (1.78mmol/L) for subjects aged 12 years and older during the washout period may be dispensed lanthanum carbonate for Part 3 at a daily dose determined by the Investigator based on serum phosphorus levels taken at each study visit up to a maximum daily dose of 3000mg which will be taken with meals.

If phosphate levels do not reach the required levels then the subject cannot enter the second treatment period of Part 2, however they can proceed to Part 3.

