## 9.3 Statistical Analysis Process

Details regarding the statistical methods and definitions will be provided in the statistical analysis plan.

To preserve the integrity of the statistical analysis and study conclusions, the statistical plan will be finalized prior to database lock.

PRA International will perform all pre-defined statistical analyses after the database is locked. Statistical analyses of efficacy and safety data will be performed using Version 9.1 or higher of SAS® (SAS Institute, Cary, NC 27513).

All data will be summarized overall.

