## 9.5 Selection of Subjects to be Included in the Analyses

**Screened Set** – The set of subjects who have signed informed consent.

**Enrolled Set** – Subjects who have signed informed consent and have begun some study procedures (eg, dispensed investigational product, current drug has been withdrawn).

**Safety Analysis Set 1** – Enrolled subjects who have taken 1 dose of investigational product in Part 1 and who have completed at least 1 follow-up safety assessment.

**Safety Analysis Set 2** – Enrolled subjects who have taken 1 dose of investigational product in Part 2 or Part 3 and who have completed at least 1 follow-up safety assessment.

It is noted that safety assessments from the period when a subject is exposed to calcium carbonate will be summarized for calcium carbonate treatment. Safety assessments from the

period when a subject is exposed to lanthanum carbonate will be summarized for lanthanum carbonate treatment.

**Safety Completer Set (SCS)** – Subjects who receive at least 8 weeks of lanthanum carbonate treatment from either Part 2 or Part 3 of the study.

**Full Analysis Set (FAS)**–Subjects who have taken at least 1 dose of investigational product and who have at least 1 phosphate assessment during Part 2 or Part 3.

**Per-protocol Set 1 (PP1)** – Subjects in the Full Analysis Set who complete 8 weeks of calcium carbonate treatment followed by 8 weeks of lanthanum carbonate treatment and who have serum phosphate assessment data available to allow summarizing the percentage of subjects achieving age-specific KDOQI target. Only subjects who have serum phosphate levels equal to or above the age-specific KDOQI targets at study entry and between the calcium carbonate treatment and lanthanum carbonate treatment at Visit 2.4 will be included in this set.

**Per-protocol Set 2 (PP2)** – Subjects in the Full Analysis Set who complete 8 weeks of treatment with lanthanum carbonate and who have serum phosphate assessment data available to allow summarizing the percentage of subjects achieving age-specific KDOQI target. Subjects who have serum phosphate levels equal to or above the age-specific KDOQI targets prior to the start of lanthanum carbonate treatment will be included in this set.

**Pharmacokinetic Set 1** - Subjects in the Safety Analysis Set 1 for whom the primary pharmacokinetic data are considered sufficient and interpretable. Subjects in Part 1 who vomited may be excluded from Pharmacokinetic Set 1.

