- The age group categories that will be summarized for the “by Age” summary tables for Subject Disposition, Demographic and Baseline Characteristics and Adverse Events have been clarified and now explicitly align with the age groups upon which the primary and secondary endpoints are analysed (≥ 10 to <12 years and ≥12 to <18 years vs. <12 years and ≥12 years).
- The study will enrol at least 32 (rather than 35) subjects who complete 8 weeks of treatment with lanthanum carbonate and are assessable for the primary endpoint.
- The definitions of PP1 and PP2 will only include subjects who have serum phosphate levels above the age-specific KDOQI target (rather than equal to or above).

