## 2. Definition of Evaluable Subjects in Per-Protocol Analysis Set 1 for Primary Endpoint Assessment

Evaluable subjects in per-protocol 1 population will be defined similar to evaluable subject in per-protocol 2 population, see above, with subjects meeting the following criteria to be deemed eligible for the per-protocol 1 population:

- Aged 10 years to <18 years of age at the time of consent
- Confirmed serum phosphorus level at study entry and between the calcium carbonate treatment and lanthanum carbonate treatment at Visit 2.4 or unscheduled visits in part 2 (Baseline Phosphorus)
  - Subjects who participated in Part 2a and received calcium carbonate, baseline serum phosphorus must be drawn after a washout period of up to 3 weeks
- Baseline serum phosphorus levels above KDOQI recommendations:
  - Age <12 years: Serum phosphorus >6.0mg/dL (1.94mmol/L)
  - Age  $\geq$ 12 years and older: Serum phosphorus >5.5mg/dL (1.78mmol/L)
- Demonstration of 8 weeks of Calcium Carbonate therapy followed by 8 weeks of Lanthanum therapy
- Confirmed serum phosphorus level after 8 weeks of Calcium Carbonate therapy followed by 8 weeks of Lanthanum therapy
- Both baseline and 8 weeks serum phosphorus levels are assessed at the same lab (central or local lab)

- Subjects, who received Calcium Carbonate and Lanthanum Carbonate therapy in part 2 or part 3 but did not receive 8 weeks of continuous treatment because of temporary dose interruption due to hypophosphatemia (protocol Appendix 2: guidelines for phosphorus and calcium levels), will be considered evaluable, if they qualify other criteria mentioned above (eg baseline phosphate > KDOQI target).

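### PP1 conditions the calcium carbonate results on phosphate measured at or after the calcium endpoint, and SAP section 17 does not list the visits added to the PP1 rule

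*SAP*

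**What the plan says.** **Outcome.** SAP 10.3 summarises, for each treatment, the percentage of subjects at or below the age-specific phosphorus target after eight weeks (5.5 mg/dL from age 12, 6.0 mg/dL below it), and the changes from baseline in phosphorus, calcium and their product. PP1 and the FAS are both used. Protocol 7.1.2.3 makes Visit 2.4 the Week 8 calcium visit in Part 2a, with a biochemistry sample.

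**PP1 rule.** Besides completing both treatments, the subject needs phosphate beyond target at entry and again before lanthanum. The second condition is worded in three ways:

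- Protocol 9.5 and the Synopsis: "between the calcium carbonate treatment and lanthanum carbonate treatment at Visit 2.4 will be included in this set".
- SAP 4.5: "at study entry and between the calcium carbonate treatment and lanthanum carbonate treatment at Visit 2.4 or the visits during washout will be included".
- SAP 21.1, item 2: "between the calcium carbonate treatment and lanthanum carbonate treatment at Visit 2.4 or unscheduled visits in part 2 (Baseline Phosphorus".

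**Path after calcium.** Subjects still above the threshold at Visit 2.4 may start lanthanum. For the others, Protocol 7.1.2.3 says: "If phosphate levels are below these levels the subject must enter a washout period of up to 3 weeks". Protocol 7.1.2.4 then holds two statements: "Subjects who complete the 3-week washout (W2) will be dispensed lanthanum carbonate", and "If phosphate levels do not reach the required levels then the subject cannot enter the second treatment period of Part 2".

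**Declared changes.** Protocol 9.3 leaves detail to the SAP: "Details regarding the statistical methods and definitions will be provided in the statistical analysis plan". On the per-protocol sets, SAP section 17 lists one change of definition: "The definitions of PP1 and PP2 will only include subjects who have serum phosphate levels above the age-specific KDOQI target", in place of at-or-above. It does not mention the washout or unscheduled visits.

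**Outputs.** Tables 3.1.2.1 and 3.1.3.1 to 3.1.3.3 use PP1, and Tables 3.1.2.2 and 3.1.3.4 to 3.1.3.6 are the FAS counterparts. Figures 3.1.3.1 to 3.1.3.3, the bar charts by treatment, are listed for PP1 only.

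**The concern.** A set that reports the calcium response should not depend on that response. Here the value that defines success on calcium is also a value that can admit a subject to the set, and success fails that test. Responders get in only through a later rebound. The lanthanum column has no such condition on its own Week 8 value, so an outcome-selected column stands beside one that is not selected in this way.

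What is at stake is how secondary objectives 2 and 4 read when PP1 is used, above all in the bar charts, which have no FAS version. The declaration gap matters because the added visits decide whether calcium responders can enter PP1 at all. A reader who relied on section 17 would not learn that this part of the rule had moved.

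**Working it through.** The plan gives no figure to reproduce, so the check compares the wording and then sizes one step.

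**Step 1: who enters PP1 under each rule**

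| Visit 2.4 phosphate | Protocol 9.5, literal | SAP 4.5 / 21.1 |
|---|---|---|
| Above target (calcium non-responder) | Qualifies | Generally qualifies on that value |
| At or below target (responder), rebounds in washout | Does not qualify | Qualifies |
| At or below target (responder), no rebound | Does not qualify | Does not qualify |

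A value exactly at target is a boundary exception: the protocol rule is at-or-above, and SAP 21.1 section 1.2 still tests at-or-above although section 17 declares strictly above. The literal protocol rule would leave essentially no calcium responders in PP1. The SAP rule restores those who rebound.

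The word *generally* is needed for two reasons. SAP 21.1 takes the central value closest to first lanthanum and makes a subject non-evaluable if that value is not above target. These steps are written for PP2 and reach PP1 because item 2 says PP1 is handled similarly. Item 2 also says that baseline in Part 2a is drawn after a washout of up to three weeks. A later value, or a central/local disagreement, could therefore remove a non-responder too.

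**Step 2: size of the selection step alone**

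Inputs, neither given in the documents:

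- *p*: calcium response at Visit 2.4 among subjects otherwise eligible for PP1.
- *r*: share of those responders left out for not rebounding.

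Response seen in PP1 = p(1 − r) / (1 − pr). At p = 50%, r = 10%: 0.45 / 0.95 = 47.4%.

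| Assumed p | r = 5% | r = 10% | r = 20% |
|---|---|---|---|
| 30% | 28.9% | 27.8% | 25.5% |
| 50% | 48.7% | 47.4% | 44.4% |
| 70% | 68.9% | 67.7% | 65.1% |

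Over p = 30% to 70% the downward shift is 1.1 to 1.3 points at r = 5%, 2.2 to 2.6 at 10%, and 4.5 to 5.6 at 20%. Inclusion criterion 5 (Protocol 4.1) argues for a small r: every entrant had already exceeded the same threshold after at most three weeks of washout. It does not show that r is zero, and the documents set no ceiling. At p = 50%, r = 50% would give 0.25 / 0.75 = 33.3%.

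**Step 3: net direction**

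Let non-responders be retained at *c* times the responders' rate for other reasons, such as lanthanum completion or the central-value rule. Response seen = p(1 − r) / [p(1 − r) + (1 − p)c], which equals p when c = 1 − r. At p = 50%, r = 10%:

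- c = 1.1: 0.45 / (0.45 + 0.55) = 45.0%
- c = 1.0: 0.45 / (0.45 + 0.50) = 47.4%
- c = 0.9: 0.45 / (0.45 + 0.45) = 50.0%
- c = 0.8: 0.45 / (0.45 + 0.40) = 52.9%

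**Step 4: in subjects**

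With an assumed 20 calcium completers and 10 responders, r = 10% is one subject: 9/19 = 47.4% (exact 95% CI 24.4 to 71.1) against 10/20 = 50% (27.2 to 72.8).

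The changes from baseline pass through the same filter, but the documents give no phosphate distribution from which to size them.

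**The case against.** The strongest reply is that the population is intended. Objectives 2 and 4 concern the calcium-then-lanthanum sequence, so restricting PP1 to subjects who completed both and were hyperphosphatemic before lanthanum suits a paired description. SAP 10.3 plans every secondary endpoint on the FAS as well, so a missing FAS bar chart withholds no number. Part of the exclusion is built into the design, since Protocol 7.1.2.4 bars non-rebounders from the second treatment period. PP1 is not the primary set, and the comparison is descriptive.

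Most of this stands. It is a good reason to keep the paired PP1 outputs rather than replace them. It does not remove the selection from the PP1 calcium column, and it does not give the bar charts a version without it.

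Three stronger readings are tempting but not supported:

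- *The SAP introduced a selection against calcium.* Its wording admits responders whom the literal protocol rule would leave out. Protocol 9.3 allows the SAP to add detail, and the added visits are stated openly in SAP 4.5 and 21.1. What is missing is an entry in section 17.
- *PP1 understates calcium overall.* Step 3 shows that other retention differences can cancel or reverse the shift.
- *The PP1 outputs carry no warning.* SAP section 1 places the output specifications in a separate document, which is not available here, so a footnote may already exist.

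**Conclusion.** PP1 selects the calcium results on the calcium outcome, and SAP section 17 omits the added washout and unscheduled visits. Both follow from the wording. The selection belongs to the PP1 concept and in part to the entry bar after washout; the SAP reduces it.

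Size and net direction are unknown. Taken alone, the step lowers the calcium response by about 1 to 6 points if 5% to 20% of responders do not rebound and the response rate lies between 30% and 70%. All of these rates are assumptions. In a group of about 20, also an assumption, a 10% loss is one subject and lies well inside the confidence interval. The effect on change from baseline is not sized.

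The primary endpoint, which rests on PP2, and the FAS tables do not carry this condition. The point concerns secondary, descriptive outputs. It is worth considering for clarity of reporting and does not threaten the trial's main result.

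**What to change.** 1. Keep the paired PP1 outputs. If the table shells do not already say so, add a footnote that the set is selected on post-calcium phosphate.
2. Add FAS versions of Figures 3.1.3.1 to 3.1.3.3. As a supplementary row or column, give the calcium result in Part 2a subjects who were above target at entry and have eight weeks of calcium and a Visit 2.4 value. Set no condition on Visit 2.4 or washout phosphate. Do not require lanthanum completion either, because the entry bar would then bring the exclusion back.
3. Report how many calcium responders were left out of PP1 for not rebounding. Listings 2.1.2 and 6.1 should hold most of what is needed.
4. Declare the added washout and unscheduled visits in SAP section 17, and align the PP1 wording across the protocol Synopsis, Protocol 9.5, SAP 4.5 and SAP 21.1 item 2.
5. Reconcile the two statements in Protocol 7.1.2.4 on subjects who complete washout without reaching the threshold, since they bear on who can enter PP1.

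The cost is some wording, three figures, a supplementary result and one count, all from data already planned for collection. The supplementary calcium result is unpaired, has a different denominator from the lanthanum column and will lie closer to the FAS result. The retained PP1 outputs keep the within-subject view.
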